**Table 2: Baseline Assessment**

Parameter	Study Assessments					Baseline Used in Data Display		
	Screening	D 1	D 4	D 15	D 18	Treatment Period 1	Treatment Period 2	Treatment Period 3
12-Lead ECG#	T #	X	X	X	X	D 1 (Pre-Dose)	D 4 (Pre-Dose)	D 15 (Pre-Dose)
Clinical chemistry^	X	X	X	X	X	D 1 (Pre-Dose)	D 4 (Pre-Dose)	D 15 (Pre-Dose)
Hematology^	X	X	X	X	X	D 1 (Pre-Dose)	D 4 (Pre-Dose)	D 15 (Pre-Dose)
Vital signs*	X	X	X	X	X	D 1 (Pre-Dose)	D 4 (Pre-Dose)	D 15 (Pre-Dose)

# T = Triplicate At Screening, triplicate ECGs are taken. Single ECGs will be taken on other scheduled days.

On Day 1, day 4 and day 15 ECG should be performed within 15 minutes before dosing and recorded in the eCRF.

^ Laboratory assessments to be performed at Screening, and prior to dosing on Day 1 of Treatment Period 1, Day 4 of Treatment Period 2 and Day 15 of Treatment Period 3.

\* To be performed within 4 hours prior to the first dosing on Day 1 of Treatment Period 1, Day 4 of Treatment Period 2 and Day 15 of Treatment Period 3. Where a measurement is abnormal or significantly different from previous measurements, a further 2 readings will be taken. When vital signs are measured in triplicate, values should be taken at least 1 minute but not more than 5 minutes apart and recorded in the CRF.

## 4.2. Primary Endpoint(s) Analyses

The primary objective of this study is to assess the effect of steady state exposure of GSK3036656 on the single dose PK of EE and LNG in healthy female participants of non-childbearing potential aged 18 to 65 years, who are missing no more than one 20 mg dose of GSK3036656 in treatment period 2 and are 100% compliant with study treatments in treatment periods 1 and 3. For the analyses planned in the following section, the potential intercurrent events that will be considered are participants missing a dose of Microgynon in treatment periods 1 and 3, or missing dose of GSK3036656 in treatment period 3, or missing more than one 20 mg dose of GSK3036656 in treatment period 2. Events leading to missing data are: participant withdrawal from study/ loss to follow-up, or missing PK assessments.

### 4.2.1. Definition of endpoint(s)/estimands

The primary pharmacokinetic endpoints and attributes of the estimand are detailed in Section 1.1. and Section 4.2.1.1

#### 4.2.1.1. Pharmacokinetic Parameters

The PK parameters will be provided by CPMS group, Parexel. The PK parameters will be calculated by NCA methods from the concentration-time data using Phoenix® WinNonlin® Version 8.3 or later following these guidelines:

- Actual time from dose will be used in the calculation of all derived PK parameters.
- There will be no imputation of missing data.
- Handling of NQ samples for derivation of plasma PK parameters after each dose administration
  - NQs at the beginning of a participant profile (i.e., before the first incidence of a measurable concentration) will be assigned to zero.
  - NQs at the end of a participant profile (i.e., after the last incidence of a measurable concentration) will be set to missing.
  - Single NQs which fall between two measurable concentrations will be set to missing.
  - Consecutive NQs which fall between measurable concentrations will be set to missing. Measurable concentrations after consecutive NQs will also be set to missing.

If a participant experiences emesis, the data for the affected period will be excluded from summary statistics and statistical analysis if vomiting occurs at or before 2 times median  $T_{max}$

The primary and secondary PK parameters (see Section 1.1 and Section 4.3.1) will be estimated according to the guidelines presented in [Table 3](#).

**Table 3: Pharmacokinetic Parameter and Estimation**

Parameter	Guideline for Derivation	Analyte
$C_{max}$ , $T_{max}$ , $C_\tau$	Obtained directly from the observed concentration-time data.	
 
• <math>C_{max}</math> and <math>T_{max}</math>: EE and LNG (Treatment Periods 1 and 3) and GSK3036656 (Treatment period 3)
 
• <math>C_\tau</math>: GSK3036656 (at Day 8, 10, 12, 15 and 16).
 

$AUC_{(0-t)}$	The AUC from zero time (predose) to the time of last quantifiable concentration will be calculated by a combination of linear and logarithmic trapezoidal methods. The linear up/log down trapezoidal method will be employed. $AUC_{(0-t)} = \int_0^t C(x) dx$	EE and LNG (Treatment Periods 1 and 3)
$AUC_{(0-\tau)}$	The AUC over the dosing interval will be determined for multiple dose studies using the same trapezoidal rule as for $AUC_{(0-t)}$ . If extrapolation is required for $AUC_{(0-\tau)}$ calculation and it is not possible to derive an acceptable $\lambda_z$ value, then AUC up to the time of last quantifiable concentration ( $AUC_{(0-t)}$ ) will be used as approximate estimate of $AUC_{(0-\tau)}$ . This imputation will be considered reliable only if the time of last measurable concentration is close to the end of the dosing interval.	GSK3036656 (Treatment Period 3)
$AUC_{(0-\infty)}$	The area from zero time extrapolated to infinite time will be calculated as follows: $AUC_{(0-\infty)} = AUC_{(0-t)} + C_{last}/\lambda_z$ where $C_{last}$ is the last observed quantifiable concentration.	EE and LNG (Treatment Periods 1 and 3)

Parameter	Guideline for Derivation	Analyte
%AUC ex	
The percentage of AUC(0-inf) obtained by extrapolation will be calculated as follows:
 $\%AUC_{ex} = (AUC(0-\text{inf}) - AUC(0-t))/AUC(0-\text{inf}) \times 100$ 
If the %AUCex is greater than 20% the value, %AUCex, and all dependent parameters will be flagged in listings. It is acceptable to include data from profiles with >20% extrapolated area if at least 80% of the profiles in the study have <20% of the AUC(0-inf) as extrapolated area. Unless otherwise determined by PK scientist's best knowledge and judgement, it is unacceptable to use AUC(0-inf) data if >40% of the AUC has been extrapolated: in this case, %AUCex, and all dependent parameters will be flagged in listings and might be excluded from summary tables and statistical analysis of PK parameters. The reason for exclusion will be listed/footnoted in parameter listings.
	EE and LNG (Treatment Periods 1 and 3)
$\lambda_z$ and $t_{1/2}$	
The apparent terminal phase rate-constant (<math>\lambda_z</math>) will be estimated by linear regression of concentration versus time data presented in a log-linear scale (with uniform weighting). Only those data points that are judged to describe the terminal log-linear decline will be used in the regression. Data points may be dropped from the linear regression if the PK Scientist considers the reported values to be anomalous. Any data points so designated should remain in the listings with a footnote and be identified in the study report with a rationale for exclusion. A minimum number of three data points in the terminal phase will be used in calculating <math>\lambda_z</math> with the line of regression starting at any post-Cmax data point (Cmax will not be part of the
	EE and LNG (Treatment Periods 1 and 3)

Parameter	Guideline for Derivation	Analyte
	
regression slope). Based on the PK Scientist's best knowledge and judgment, if the adjusted coefficient of determination (<math>R^2</math> adjusted) is <math><0.85</math>, then <math>\lambda_z</math> and all the <math>\lambda_z</math> dependent parameters (i.e. <math>t_{1/2}</math>, <math>AUC_{(0-\infty)}</math>) will be flagged in listings and might be excluded accordingly from summary tables and statistical analysis of PK parameters. The reason for flagging/exclusion will be listed/footnoted in parameter listings.
 
The interval used to determine <math>\lambda_z</math> should be equal or greater than 2-fold the estimated <math>t_{1/2}</math>, and if less than 2-fold, <math>\lambda_z</math> will be flagged in listings. All the derived parameters (i.e. <math>t_{1/2}</math>, <math>AUC_{(0-\infty)}</math>) will also be flagged in listings. The reason for flagging will be listed/footnoted in parameter listings.
 
The <math>t_{1/2}</math> will be calculated as follows:
 $t_{1/2} = \ln 2 / \lambda_z = 0.693 / \lambda_z$	

#### 4.2.2. Main analytical approach

The primary analysis for the primary PK endpoints will be performed for the strata of participants able to adhere to treatment as defined in primary estimand framework, and included in the PK analysis set.  $\tau$

- Based on the individual concentration-time data the following primary plasma parameters will be estimated, refer Section 4.2.1.1. Pharmacokinetic Parameters for more details:
  - EE (separately for Microgynon+GSK3036656 and Microgynon alone):  $AUC_{(0-\infty)}$  and  $C_{max}$
  - LNG (separately for Microgynon+GSK3036656 and Microgynon alone):  $AUC_{(0-\infty)}$  and  $C_{max}$

- Analyses will be performed on the natural logarithms of  $AUC_{(0-\infty)}$  and  $C_{max}$ , for EE and LNG, separately using linear mixed effect models with treatment as a fixed effect and subject as a random effect. Effects will be estimated, and CIs will be constructed for the following treatment comparison:
  - Microgynon+GSK3036656 (Treatment Period 3) versus Microgynon alone (Treatment Period 1)
- Point estimates and 90% CIs for treatment differences on the log scale derived from the model will be exponentiated to obtain estimates for geometric mean ratios and CIs on the original scale.

Summary statistics for plasma EE and LNG PK parameter values will be presented by treatment, refer to Section 4.1.1 General Methodology and Section 4.3.1.2.5 Pharmacokinetic Parameter Summary Tables for more details.

#### **4.2.3. Sensitivity analyses**

- Not applicable

#### **4.2.4. Additional estimands**

- Not applicable

### **4.3. Secondary Endpoint(s) Analyses**

#### **4.3.1. Secondary Pharmacokinetics Endpoints**

Secondary PK objectives for this study are to characterize the steady state PK of GSK3036656 in the presence of EE/LNG and to characterize the single dose PK of EE/LNG alone and in the presence of GSK3036656, in healthy female participants.

##### **4.3.1.1. Definition of [endpoint(s)/estimands]**

The secondary Pharmacokinetic endpoints and attributes of the estimands are detailed in in Section 1.1

Refer to Section 4.2.1.1 Pharmacokinetic Parameters for more details.

#### 4.3.1.2. Main analytical approach (Pharmacokinetic analysis)

- The analysis for the secondary PK endpoints will be performed for the participants included in the PK analysis set.
- Based on the individual concentration-actual time data the following secondary plasma parameters will be estimated, as data permits (refer to Section 4.2.1.1 Pharmacokinetic Parameters for more details):
  - EE and LNG (separately for Microgynon+GSK3036656 and Microgynon alone):  $AUC_{(0-t)}$ ,  $T_{max}$  and  $t_{1/2}$
  - GSK3036656 (Microgynon+GSK3036656):  $AUC_{(0-\tau)}$ ,  $C_{max}$ ,  $T_{max}$ , and  $C_\tau$  (Day 8, 10, 12, 15 and 16).
  - GSK3036656 (GSK3036656 alone): Whilst not defined as a secondary endpoint  $C_\tau$  (Day 8, 10 and 12), will also be analysed to aid in interpretation on achievement of steady state.
    - Analyses will be performed on the natural logarithms of GSK3036656  $C_\tau$ , separately using mixed effect models with day (include Day 8, 10, 12, and 15 pre-dose concentration) as a fixed effect and subject as a random effect.
    - The coefficients of the slopes for the day effect on log scale, along with corresponding 90% confidence intervals, will be used to determine whether steady state was achieved prior to co-administration with EE and LNG.

Summary statistics for plasma EE, LNG, and GSK3036656 PK parameter values will be presented by treatment, refer to Section 4.1.1 General Methodology and Section 4.3.1.2.5 Pharmacokinetic Parameter Summary Tables for more details.

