### **Primary estimands of secondary Pharmacokinetic endpoints**

#### **Steady State PK of GSK3036656**

The clinical question of interest is:

What are the estimates (mean/ median and variability) of steady state PK parameters (AUC(0- $\tau$ ), Cmax, C $\tau$  and Tmax) of GSK3036656 in the presence of EE/LNG in healthy female participants, who are missing no more than one 20 mg dose of GSK3036656 in treatment period 2 and are 100% compliant with study treatments in treatment period 3?

The Primary Estimand is described by the following attributes:

- Population: Healthy female participants of non-childbearing potential aged 18 to 65 years.
- Endpoints: AUC(0- $\tau$ ), Cmax, C $\tau$  and Tmax for GSK3036656
- Treatments: single dose Microgynon+14 days GSK3036656
- Strategy for intercurrent event: The intercurrent events of interest are participants missing their dose of Microgynon during treatment period 3, or missing a dose of GSK3036656 in treatment period 3, or missing more than one 20 mg dose of GSK3036656 in treatment period 2. The strategy for handling all of these intercurrent events will be a Principal Stratum Strategy, where we are only interested in the strata of participants who are missing no more than one 20 mg dose of GSK3036656 in treatment period 2 and are 100% compliant with study treatments in treatment period 3.
- Population-level summary:
  - For AUC(0- $\tau$ ), Cmax, and C $\tau$  of GSK3036656: Descriptive Statistics (including n, Arithmetic means with 95% CI, Geometric means with 95% CI, CV%, SD, Median with Min, Max);
  - for Tmax of GSK3036656: Descriptive Statistics (including n, Median with Min, Max).

Rationale for estimand: Interest lies in estimating the pharmacokinetics of GSK3036656 in the presence of Microgynon, which cannot be accurately assessed in the situation where participants are missing more than one 20 mg dose of GSK3036656 in treatment period 2 and are not 100% compliant with study treatments in treatment period 3.

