## Primary estimands of secondary Pharmacokinetic endpoints

### Steady State PK of GSK3036656

The clinical question of interest is:

What are the estimates (mean/ median and variability) of steady state PK parameters ( $AUC_{(0-\tau)}$ ,  $C_{max}$ ,  $C_\tau$  and  $T_{max}$ ) of GSK3036656 in the presence of EE/LNG in healthy female participants, who are missing no more than one 20 mg dose of GSK3036656 in treatment period 2 and are 100% compliant with study treatments in treatment period 3?

The Primary Estimand is described by the following attributes:

- Population: Healthy female participants of non-childbearing potential aged 18 to 65 years.
- Endpoints:  $AUC_{(0-\tau)}$ ,  $C_{max}$ ,  $C_\tau$  and  $T_{max}$  for GSK3036656
- Treatments: single dose Microgynon+14 days GSK3036656
- Strategy for intercurrent event: The intercurrent events of interest are participants missing their dose of Microgynon during treatment period 3, or missing a dose of GSK3036656 in treatment period 3, or missing more than one 20 mg dose of GSK3036656 in treatment period 2. The strategy for handling all of these intercurrent events will be a Principal Stratum Strategy, where we are only interested in the strata of participants who are missing no more than one 20 mg dose of GSK3036656 in treatment period 2 and are 100% compliant with study treatments in treatment period 3.
- Population-level summary:
  - For  $AUC_{(0-\tau)}$ ,  $C_{max}$ , and  $C_\tau$  of GSK3036656: Descriptive Statistics (including n, Arithmetic means with 95% CI, Geometric means with 95% CI, CV%, SD, Median with Min, Max);
  - for  $T_{max}$  of GSK3036656: Descriptive Statistics (including n, Median with Min, Max).

Rationale for estimand: Interest lies in estimating the pharmacokinetics of GSK3036656 in the presence of Microgynon, which cannot be accurately assessed in the situation where participants are missing more than one 20 mg dose of GSK3036656 in treatment period 2 and are not 100% compliant with study treatments in treatment period 3.

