## Pharmacokinetics of EE/LNG

The clinical question of interest is:

What are the estimates (mean/ median and variability) of the PK parameters ( $AUC_{(0-t)}$ ,  $T_{max}$  and  $t_{1/2}$ ) of EE and LNG with and without GSK3036656 in healthy female participants, who, for the estimates with GSK3036656 are missing no more than one 20 mg dose of GSK3036656 in treatment period 2 and are 100% compliant with doses of GSK3036656 in treatment period 3? For the estimates of PK parameters of EE and LNG taken alone, no intercurrent events are defined.

The Primary Estimand is described by the following attributes:

- Population: Healthy female participants of non-childbearing potential aged 18 to 65 years.
- Endpoints:  $AUC_{(0-t)}$ ,  $T_{max}$ , and  $t_{1/2}$  for EE and LNG
- Treatments: single dose Microgynon+ 14 days GSK3036656 and single dose Microgynon

Strategy for intercurrent event: The intercurrent events of interest, applicable to estimates of PK parameters for EE and LNG with GSK3036656 only, is participants missing one or more doses of GSK3036656 in treatment period 3, or missing more than one 20 mg dose of GSK3036656 in treatment period 2. The strategy for handling this intercurrent events will be a Principal Stratum Strategy, where we are only interested in the strata of participants who are missing no more than one 20 mg GSK3036656 dose in treatment period 2 and are 100% compliant with doses of GSK3036656 in treatment period 3. For the estimates of PK parameters of EE and LNG taken alone, no intercurrent events are defined.

- Population-level summary:
  - For  $AUC_{(0-t)}$  and  $t_{1/2}$  (h) of EE and LNG: Descriptive Statistics (including n, Arithmetic means with 95% CI, Geometric means with 95% CI, CV%, SD, Median with Min, Max);
  - for  $T_{max}$  of EE and LNG: Descriptive Statistics (including n, Median with Min, Max).

Rationale for estimand: Interest lies in estimating the pharmacokinetics of Microgynon, with and without GSK3036656. The PK of Microgynon taken with GSK3036656 cannot be accurately assessed in the situation where participants are missing more than one 20 mg dose of GSK3036656 in treatment period 2 or are not compliant with doses of GSK3036656 in treatment period 3.

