## 3. ANALYSIS SETS

Analysis Set	Definition / Criteria	Analyses Evaluated
Screened	
 
• All participants who signed the ICF and were screened for eligibility.
 
• This population will be used for screen failure listing and summary.
 
	Study Population
Enrolled	
 
• All participants who entered the study (who received study intervention or underwent a post screening study procedure).
 
• Note screening failures (who never passed screening even if rescreened) and participants screened but never enrolled into the study (Met eligibility but not needed) are excluded from the Enrolled analysis set as they did not enter the study.
 
	Study Population
Safety	
 
• All participants who received at least 1 dose of study medication.
 
• Participants will be analyzed according to the actual study intervention.
 
	Safety

Analysis Set	Definition / Criteria	Analyses Evaluated
	
 
This population will be used for all demographic and safety summaries and listings.
 
	
PK	
 
All participants in the Safety analysis set who had at least 1 non-missing PK assessment (NQ values will be considered as non-missing values).
 
Data will be reported according to the actual study intervention.
 
This population will be used for PK summary tables, statistical analysis tables, figures, and listings.
 
	PK

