#### **4.3.1.2.5. Pharmacokinetic Parameter Summary Tables:**

Biostatistics group will consider the derived PK parameters as source data and will use this data without rounding for calculation of PK parameters summary statistics tables.

The PK parameters will be summarized by analyte, treatment, and day for the PK analysis set; for more details, refer to Section 4.1.1 General Methodology.

PK parameters that are not determined (ND) because the planned calculation could not be adequately performed will be assumed missing in both descriptive and statistical analyses and no imputation will be performed.

In case of  $C_t$  concentrations that are NQ, for PK parameter summary tables they will be handled with the same rules described as for concentration summary tables.

Data in PK parameter summary tables will be reported as per IDSL reporting standards.

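### The secondary PK analyses run on the full PK analysis set, although their estimands cover only dose-compliant participants (GSK3036656 PK and Period 3 EE/LNG PK)

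*SAP*

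**What the plan says.** **Estimands (SAP 1.1, protocol Section 3).** Both secondary PK estimands use a principal stratum strategy.

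- Steady-state GSK3036656 PK: "we are only interested in the strata of participants who are missing no more than one 20 mg dose of GSK3036656" in Period 2, with full compliance with study treatments in Period 3. The protocol's rationale is that this PK is something "which cannot be accurately assessed in the situation where participants are missing more than one 20 mg dose of GSK3036656 in treatment period 2".
- EE/LNG PK with GSK3036656: "we are only interested in the strata of participants who are missing no more than one 20 mg GSK3036656 dose in treatment period 2", with full compliance with GSK3036656 doses in Period 3.
- EE/LNG alone (Period 1): "For the estimates of PK parameters of EE and LNG taken alone, no intercurrent events are defined".

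**Analysis text.** SAP 4.3.1.2 states: "The analysis for the secondary PK endpoints will be performed for the participants included in the PK analysis set". Protocol 9.3.3.1.1 has the same sentence. For the summary tables, SAP 4.3.1.2.5 states: "The PK parameters will be summarized by analyte, treatment, and day for the PK analysis set". SAP Section 3 defines that set as "All participants in the Safety analysis set who had at least 1 non-missing PK assessment", and non-quantifiable values count as non-missing.

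**Primary analysis, for contrast.** SAP 4.2.2 and protocol 9.3.2.2 say that it "will be performed for the strata of participants able to adhere to treatment as defined in primary estimand framework", and add membership of the PK analysis set as a second condition.

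**The concern.** The estimand says who the question is about, and the analysis section says who is counted. Here the two differ. GSK3036656 is taken at home for much of Period 2, whereas inpatient doses are given under supervision (protocol 6.4). The participant who matters in practice is therefore one who misses two or more home doses in Period 2 and still completes Period 3.

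For her, the plan as written has two results:

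- Her Period 3 EE/LNG profile leaves the primary AUC(0-inf) and Cmax models but stays in the AUC(0-t), Tmax and t1/2 summaries. Her GSK3036656 profile also stays in the steady-state summaries. The sponsor's own rationale calls such data unsuitable for the question.
- SAP 4.2.2 sends the descriptive statistics for the primary EE/LNG parameters to 4.3.1.2.5, which uses the full PK set. The geometric means shown for AUC(0-inf) and Cmax could then come from different participants than the ratio beside them.

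If the population is settled only after it is known who missed doses, the choice is open to the criticism that it was driven by the data.

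**Working it through.** **1. The populations side by side**

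| Analysis | Estimand population | Population in the analysis text |
|---|---|---|
| Primary EE/LNG AUC(0-inf), Cmax | Compliant stratum | Compliant stratum and PK set (SAP 4.2.2, protocol 9.3.2.2) |
| GSK3036656 AUC(0-tau), Cmax, Tmax, Ctau | Compliant stratum | PK set only (SAP 4.3.1.2, 4.3.1.2.5, protocol 9.3.3.1.1) |
| Period 3 EE/LNG AUC(0-t), Tmax, t1/2 | Compliant stratum | PK set only (same sections) |
| Period 1 EE/LNG AUC(0-t), Tmax, t1/2 | No intercurrent events defined | PK set: consistent |

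Only the second and third rows conflict. The emesis rule in SAP 4.2.1.1 and the extrapolation and terminal-slope rules in SAP Table 3 concern data quality. They do not remove participants for missed doses.

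**2. Plan figures.** The plan gives no figure for this point. Its joint power of 91.91% concerns the primary endpoints, whose text already applies the stratum, so it does not depend on this point.

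**3. How likely such a participant is.** The documents give no non-compliance rate. If each of 20 participants independently falls outside the stratum with probability p, the chance of at least one is 1 - (1 - p)^20. An assumed p of 2.5% gives 1 - 0.975^20 = 40%; an assumed p of 20% gives 1 - 0.80^20 = 99%.

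**4. Illustrative size for GSK3036656.**

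- From the documents: 40 mg on Day 4, 20 mg daily on Days 5-14, 20 mg on Day 15, about 20 enrolled.
- Assumed, because the documents give none of it: one compartment, instantaneous absorption, half-life 12, 24 or 48 h.
- Fraction left after 24 h: q = 0.5^(24/half-life), which is 0.25, 0.5 or 0.707.
- Day 15 predose trough (amount units): T = 40q^11 + 20(q + q^2 + ... + q^10), which is 6.67, 20.0 or 47.7.
- Day 15 AUC(0-tau) is proportional to T + 20.
- Geometric-mean shift when one of 20 is affected: ratio^(1/20) - 1.

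Worked case: half-life 24 h, Days 13 and 14 missed. The trough loses 20(0.5 + 0.25) = 15 and falls from 20 to 5, a ratio of 0.25. The AUC ratio is (5 + 20)/(20 + 20) = 0.625. The shifts are 0.25^(1/20) - 1 = -6.7% for the trough and 0.625^(1/20) - 1 = -2.3% for AUC. For 12 and 48 h the same omission gives trough ratios of 0.063 and 0.493 and AUC ratios of 0.766 and 0.643.

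There are 10 × 9/2 = 45 ways to miss two of the ten 20 mg doses in Period 2. Over all 45:

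| Shift in geometric mean | 12 h | 24 h | 48 h |
|---|---|---|---|
| AUC(0-tau), median | -0.06% | -0.33% | -0.65% |
| AUC(0-tau), worst (Days 13-14) | -1.3% | -2.3% | -2.2% |
| Predose trough, median | -0.24% | -0.68% | -0.95% |
| Predose trough, worst (Days 13-14) | -12.9% | -6.7% | -3.5% |
| AUC(0-tau), Day 14 alone missed (inside the stratum) | -1.0% | -1.4% | -1.2% |
| Predose trough, Day 14 alone missed (inside the stratum) | -6.7% | -3.4% | -1.7% |

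**5. EE/LNG.** The documents give no relation between GSK3036656 exposure and EE/LNG exposure, so no effect can be calculated.

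**The case against.** The best defence is that the omission is one of drafting. SAP 4.3.1.1, immediately before the population sentence, sends the reader to Section 1.1 for the estimand attributes, and Section 1.1 states the strata clearly. The PK analysis set could then be read as the base set to which the estimand adds its condition. This is probably what was meant. It does not settle the matter, because the primary text states both conditions in one sentence. A programmer who reads 4.2.2 and then 4.3.1.2 would reasonably restrict the first analysis and not the second.

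There are also safeguards. Compliance is checked at each visit (protocol 6.4), an investigator may withdraw a participant for compliance reasons (protocol 7.2), compliance is summarised (SAP 6.1.5), and PK data are listed by participant. These make a problem visible but do not decide who enters a table.

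On size, the objection largely stands. The worst cases need the last two doses before Day 15 to be missed, and the median shifts are below 1%. The stratum itself admits one missed Day 14 dose, which produces about half or more of the worst shifts. It reduces the effect without removing it.

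A reader might infer that the steady-state trough model in SAP 4.3.1.2 also breaches an estimand. The documents do not support that: the analysis is introduced as not being a secondary endpoint, and no intercurrent-event strategy is defined for the slope. Its population is the sponsor's choice.

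**Conclusion.** The mismatch is real and appears in both documents. For GSK3036656 PK and Period 3 EE/LNG PK, the stated analysis population is wider than the estimand population. The impact is minor and confined to descriptive secondary summaries.

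A reader might infer that the interaction conclusion is at risk. It is not: the primary analysis names its own stratum, so the two one-sided tests, the power and the sample size are unchanged. Nor are the Period 1 secondary EE/LNG summaries at fault, since no intercurrent events are defined for them.

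The text comparison needs no assumption. The size does: it rests on the assumed half-lives, the simple one-compartment model, and one of 20 participants missing exactly two doses. More affected participants or more missed doses would enlarge it.

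**What to change.** Before database freeze, state in SAP 4.3.1.2 and 4.3.1.2.5 that:

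1. summaries of all GSK3036656 secondary endpoints (AUC(0-tau), Cmax, Tmax, and Ctau on Days 8, 10, 12, 15 and 16) and of Period 3 EE/LNG AUC(0-t), Tmax and t1/2 use PK analysis set participants who belong to the stratum of the matching secondary estimand;
2. summaries of EE/LNG AUC(0-inf) and Cmax that accompany the primary analysis use the primary stratum;
3. Period 1 secondary EE/LNG summaries and all listings use the full PK analysis set.

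Also state which population the concentration summary tables and the mean and median figures use (SAP 4.3.1.2.2 and 4.3.1.2.3), so that they match the parameter tables. Record the change in SAP 4.7 and align protocol 9.3.3.1.1 at the next amendment.

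The Period 3 condition should stay for the predose troughs, even though those samples precede Period 3 dosing. Ctau on those days is a listed secondary endpoint whose estimand requires that condition, so dropping it would create a new mismatch.

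The cost is a few sentences. No new data are needed, because capsule counts, the participant diary and recorded dosing deviations (protocol 6.4) already identify missed doses. The downside is that n may fall slightly in some secondary tables.
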